
Figure 6. Hazard curves for incident of Heart Failure among 5,958 MESA participants stratified according to the presence or absence of hypertension (prevalence=45%) or the presence or absence of "high" reflection magnitude (top 45% of the population). Hazard curves are adjusted for other significant predictors of HF in this population. From: [name] JA et al, *J Am Coll Cardiol*: 60:2170-2177.

Targeting Central Hemodynamics in CKD Pilot Study
Protocol Version 003, February 15, 2016

highly desirable goal from the clinical and public health perspective. In order to design a definitive proof of concept trial, we must first establish the optimal dose of ISMN to reduce wave reflections independently of blood pressure and to assess the variability in study endpoints in response to ISMN in this particular population, such that adequate power calculations can be made.

C. RESEARCH DESIGN AND METHODS

C.1. Overview of study design

This is a pilot study in which we will study 20 subjects with CKD. We will perform a run-in phase in which the dose of sustained-release ISMN (SR-ISMN) will be increased from 30 to 120 mg over weeks. We will administer 30 mg for 1 week, followed by 60 mg for 1 week, followed by 120 for 1 week. At the end of each week, we will perform detailed assessments of blood pressure and central hemodynamics. We will assign half of the participants to receive vitamin C (500 mg three times daily) to assess whether this intervention reduces nitrate tolerance.

After the initial 3-week run in phase, we will randomly assign subjects to receive either 60 or 120 mg of SR-ISMN for additional 21 weeks (for a total of 24 weeks of therapy). Half of the subjects will continue to receive vitamin C (500 mg three times daily by mouth) throughout this 21-week period. We will assess the effect of our interventions on late systolic load, LV mass, LV fibrosis, diastolic relaxation and quality of life.

After subjects are identified and demonstrate an interest in the research study, inclusion and exclusion criteria will be assessed and if eligible, the patients will undergo written informed consent and enrolled in the study.

C.2 Study Sites

The two sites for this trial will be the Hospital of the University of Pennsylvania and the Penn Presbyterian Medical Center. Both sites share a single Institutional Review Board.

C.3. Study Population

[figure not shown]

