If the drug is not tolerated, subjects will be discontinued from the study. After completion of the run-in phase, subjects will be assigned to different doses of SR-ISMN (60 and 120 mg of SR ISMN daily) for additional 21 weeks (10 subjects per dose). Patients will continue taking ascorbic acid according to their initial allocation to receive or to not receive vitamin C. The design will therefore be a 2x2 factorial, such that 5 subjects will be allocated to ISMN SR 60- mg without vitamin C, 5 subjects will be allocated to ISMN SR 60- mg with vitamin C, 5 subjects will be allocated to ISMN SR 120- mg without vitamin C, and 5 subjects will be allocated to ISMN SR 120- mg with vitamin C. The intervention will be open label, but endpoint assessments will be blinded.

C.6. 12-week visit

The 12-week visit will take place in which we will perform:

- An office BP measurement
- Arterial tonometry and VaSera measurements
- A 2d Echocardiogram
- 24 hour ambulatory BP monitoring and pulse wave analysis monitoring
- A blood draw and urine sample

C.7. Final (24-week) assessments:

After the end of the 24 weeks therapy, arterial tonometry, VaSera measurements, Doppler echocardiography, cardiac MRI, 24-hour BP / pulse wave analysis monitoring, and blood draws will be repeated after the end of 21 weeks of fixed dose ISMN SR therapy (with or without vitamin C), to assess for changes in response to the study intervention. Procedures will be identical to those performed during the baseline assessment.

C8. Adverse Event Reporting

Targeting Central Hemodynamics in CKD Pilot Study
Protocol Version 003, February 15, 2016

All adverse events will be reported following institutional guidelines. The research team will keep a log of all adverse events that occur in the trial, and any reportable events will be handled accordingly. The study team in charge of the conduct of the trial is up to date on all trainings pertaining to safety guidelines and adverse event reporting. All Serious Adverse Events will be reported to the site review boards, the Data Safety Monitoring Board, as well as the NIH in a timely fashion.

C.7. Data Management

The data for this trial will be collected by the research staff during each visit that the subject attends. Specific forms have been developed for the questions in this trial and will be filled out via pen and paper. Later, this data will be entered into a database developed in RedCap.

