The conduct of these studies will involve 20 human subjects. All subjects will be adults able to give informed consent. Subjects will be enrolled without regard to gender or race. However, an effort will be made for an enrolled population composed of at least 50% females and ~50% members of an ethnic minority according to the demographic characteristics of the Philadelphia area. Children will not be enrolled. All patients will be recruited from the Hospital of the University of Pennsylvania or the Penn Presbyterian Medical Center. The study involves various tests (cardiac MRI with gadolinium, arterial tonometry, ambulatory blood pressure / pulse wave analysis measurements, a blood draw) and the administration of ISMN and ascorbic acid therapy.

Potential Risks: There is minimal risk to the subjects. Potential risks are associated with Targeting Central Hemodynamics in CKD Pilot Study Protocol Version 003, February 15, 2016

the study tests, the study interventions (pharmacologic therapy) and potential breaches in confidentiality.

- (1) **Cardiac MRI:** The non-invasive nature and the lack of ionizing radiation make the risks associated with MRI small. A MRI scan requires the participant to be in a partially enclosed space inside the scanner. Some people may find this to be uncomfortable. Claustrophobia is an exclusion criterion for the study. The MRI scanner produces different types of noises during a scan. Participants are special earplugs to reduce the noise. A MRI scanner has a strong magnet which attracts certain metals. If anyone has these types of metal in their body, the MRI's strong magnetic field can cause them to move which may cause injury. Subjects will be thoroughly screened for the presence of body metal and excluded from the study if they are unable to safely undergo a cardiac MRI.

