c. Protection against risks associated with gadolinium contrast: Serum creatinine will be measured prior to each scan to assure adequate renal function for the administration of gadolinium-based contrast as per our inclusion/exclusion criteria. Pregnancy status will be determined for all women of childbearing age before enrollment and before the final MRI scan. Pregnant women will be excluded and/or discontinued from the study. Subjects will not receive two injections of gadolinium within one week of each other as frequent use of gadolinium can cause nephrogenic systemic fibrosis (NSF). If a subject has recently received an MRI for clinical purposes, the research MRI will be delayed to avoid the second injection of gadolinium within the one week-timeframe.

d. Protection against risks of study medications: To reduce the risk of hypotension and related side effect, participants will be instructed to get up slowly when rising from a sitting or lying position. The study team will specifically assess for the presence of Targeting Central Hemodynamics in CKD Pilot Study

Protocol Version 003, February 15, 2016

hypotension and orthostatic hypotension, as well as symptoms such as dizziness after the medication is initiated or after the dose is increased, in order to determine whether it is safe for participants to continue taking these medications, or to uptitrate the dose. If participants find these side effects too uncomfortable, they will be deemed intolerant to the drugs and discontinued from the study. Study subjects can always withdraw from the study at any time and this will be made clear to them. We will specifically exclude individuals who are taking sildenafil (Viagra®), tadalafil (Cialis®), or vardenafil (Levitra®) and we will instruct them not to take these medications while participating in the study, as well as the risks associated with this combination. If subjects express the wish to take these medications within the 24 weeks following consent, they will not be included in the study. We will exclude subjects with a history of kidney stones, since vitamin C may precipitate the recurrence of oxalate kidney stones. We will also exclude patients with G6PD deficiency, since vitamin C may precipitate hemolysis in this condition.^{72, 73}

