Geriatric Use

Clinical studies of IMDUR Tablets did not include sufficient information on patients age 65 and over to determine whether they respond differently from younger patients. Other reported clinical experience for IMDUR has not identified differences in response between elderly and younger patients. Clinical experience for organic nitrates reported in the literature identified a potential for severe hypotension and increased sensitivity to nitrates in the elderly. In general, dose selection for an elderly patient should be cautious, usually starting at the low end of the dosing range, reflecting the greater frequency of decreased hepatic, renal, or cardiac function, and of concomitant disease or other drug therapy. Elderly patients may have reduced baroreceptor function and may develop severe orthostatic hypotension when vasodilators are used. IMDUR should therefore be used with caution in elderly patients who may be volume depleted, on multiple medications or who, for whatever reason, are already hypotensive. Hypotension induced by isosorbide mononitrate may be accompanied by paradoxical bradycardia and increased angina pectoris.

Elderly patients may be more susceptible to hypotension and may be at a greater risk of falling at therapeutic doses of nitroglycerin. Nitrate therapy may aggravate the angina caused by hypertrophic car diomyopathy, particularly in the elderly.

ADVERSE REACTIONS

The table below shows the frequencies of the adverse events that occurred in >5% of the subjects in three placebo-controlled North American studies in which patients in the active treatment arm received 30 mg, 60 mg, 120 mg, or 240 mg of isosorbide mononitrate as IMDUR Tablets once daily. In parentheses, the same table shows the frequencies with which these adverse events were associated with the discontinuation of treatment. Overall, 8% of the patients who received 30 mg, 60 mg, 120 mg, or 240 mg of isosorbide mononitrate in the three placebo-controlled North American studies discontinued treatment because of adverse events.

Most of these discontinued because of headache. Dizziness was rarely associated with withdrawal from these studies. Since headache appears to be a dose-related adverse effect and tends to disappear with continued treatment, it is recommended that IMDUR treatment be initiated at low doses for several days before being increased to desired levels.

FREQUENCY AND ADVERSE EVENTS (DISCONTINUED)*

Three Controlled North American Studies					

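### The stated 10 per dose and 5 per cell after the run-in equal all 20 subjects entered, so they need zero run-in loss, for which the plan makes no allowance

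*Combined protocol and SAP*

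**What the plan says.** The total appears twice. Section C.1: "This is a pilot study in which we will study 20 subjects with CKD". Section F.1: "The conduct of these studies will involve 20 human subjects".

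Under section C.5, half the subjects are randomised to vitamin C at the start of the run-in, and ISMN is then stepped through three doses over three weeks. The rule for intolerance is: "If the drug is not tolerated, subjects will be discontinued from the study". Section F.2(d) says the same of subjects who find the side effects too uncomfortable: "they will be deemed intolerant to the drugs and discontinued from the study".

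The dose assignment comes next in C.5: "After completion of the run-in phase, subjects will be assigned to different doses of SR-ISMN", "for additional 21 weeks (10 subjects per dose"). Section C.1 makes clear that this step is random. Subjects keep their vitamin C allocation, and the cell sizes are then listed, "such that 5 subjects will be allocated to ISMN SR 60- mg without vitamin C" and likewise 5 in each of the other three.

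The text supplied has no replacement rule, no over-enrolment and no expected run-in loss. Section C.8 (Early termination) provides a termination visit only. Section D covers the analysis of dropouts, not how many subjects are assigned.

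**The concern.** The number assigned after the run-in equals the number that entered it, although the plan removes subjects in between. The stated factorial size is therefore the best case, presented as the plan.

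The order of the two allocations adds to this. Vitamin C is fixed before the run-in and dose after it, so losses can fall unevenly on the two vitamin C groups. With no replacement, any loss rules out four cells of 5. Uneven loss also rules out equal cells at a smaller size. The plan gives target counts but no mechanism that keeps dose balanced within vitamin C group when the counts change.

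At stake are the stated cell size and the number of subjects with a 24-week change. MRI is done only at baseline and week 24, so a subject removed in the run-in contributes no MRI change to the variability estimates that are to inform the definitive trial.

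**Working it through.** **Inputs.** Entering: 20 (C.1, F.1). Assigned: 10 per dose, 5 per cell (C.5). Run-in loss d: not given for this trial, so it is an assumption. The only tolerance data are in Appendix I, Adverse Reactions. The label sentence beginning "Overall, 8% of the patients who received 30 mg, 60 mg, 120 mg, or 240 mg of isosorbide mononitrate" gives 8% stopping treatment because of adverse events. The table there gives stopping for headache as 5% at 30 mg, 8% at 60 mg and 5% at 120 mg. The anchor is therefore d = 5% to 8%, with a wider range shown.

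**Step 1: reproduce the plan's figure.** 2 doses x 10 = 4 cells x 5 = 20. This equals the number entering, so it holds only if d = 0.

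**Step 2: chance of full delivery and expected number.** With independent losses, P(all 20 assigned) = (1 − d)^20, and the expected number assigned is 20(1 − d).

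| Assumed loss d | P(all 20 assigned) | Expected assigned | Per cell (÷ 4) |
|---|---|---|---|
| 1% | 0.99^20 = 82% | 19.8 | 4.95 |
| 3% | 0.97^20 = 54% | 19.4 | 4.85 |
| 5% | 0.95^20 = 36% | 19.0 | 4.75 |
| 8% | 0.92^20 = 19% | 18.4 | 4.6 |
| 10% | 0.90^20 = 12% | 18.0 | 4.5 |

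**Step 3: break-even.** (1 − d)^20 = 0.5 gives d = 1 − 0.5^(1/20) = 3.4%. Below that, full delivery is more likely than not.

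**Step 4: balance of dose and vitamin C.** Suppose nobody is lost and dose is randomised 10:10 without regard to vitamin C group. The chance of 5/5/5/5 is then C(10,5)² / C(20,10) = 252² / 184,756 = 63,504 / 184,756 = 34%. A dose list stratified by vitamin C group gives 5/5/5/5 with certainty when nobody is lost, and keeps the doses as even as possible within each group otherwise.

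**Step 5: how much imbalance matters.** One loss giving cells of 5, 5, 5 and 4 produces a dose by vitamin C correlation of (5×4 − 5×5) / √(10×9×10×9) = −5/90 = −0.06, which is negligible.

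**Step 6: effect on the variability aims.** The upper 95% limit of an SD is the estimate times √[(n − 1)/χ²(0.025; n − 1)]. This is 1.46 times at n = 20 and 1.50 times at n = 18.

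**The case against.** The strongest reply is that nothing is miscalculated. 4 x 5 is 20, the counts are planning targets, and no power calculation rests on 5 per cell. Section D already says that power is limited and that trends will be read conservatively. It also plans mixed models and approaches to dropout that tolerate unequal cells. This stands, and it keeps the point small. It does not explain how 20 subjects remain after a step that removes some of them.

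Four stronger readings are tempting, and the documents do not support them.

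- A reader might infer that the plan forbids replacement. It is silent, and part of the document was not available for review.
- A reader might infer that run-in losses must fall unevenly on the vitamin C groups. They can, but need not: two random losses from 10 + 10 split one and one with probability 10 × 10 / 190 = 53%.
- A reader might infer that dose and vitamin C will be confounded. C.5 intends an equal vitamin C split within each dose, and a single loss leaves a correlation of only about −0.06. The gap is that the means of keeping balance is not stated.
- A reader might infer that the plan will miss its size 81% of the time (100% − 19%). That takes the label's 8% as this trial's run-in loss. The label trials were in angina patients and included 240 mg. At least one ran up to 6 weeks, against 3 weeks here, and the label's 120 and 240 mg patients started at 60 mg, whereas this protocol starts at 30 mg. Loss could be lower. Withdrawal for reasons other than tolerability, foreseen in C.8, pushes the other way.

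One might also read 20 as the number completing the run-in. F.1 points against that by giving 20 as the number the studies involve. The doubt is itself a reason for a clarifying sentence.

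**Conclusion.** The point holds as an inconsistency between the number entering, the discontinuation rule and the number assigned. The stated 10 per dose and 5 per cell require zero run-in loss. Under an assumed loss of 5% to 8%, that has a probability of 36% to 19%, and about 18 to 19 subjects (4 to 5 per cell) would be expected. If loss is below about 3.4%, full delivery is more likely than not.

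The figures assume independent losses and the label rates, carried over from a different population and dose range. They also depend on who counts as lost. C.5 does not say whether a subject who fails an up-titration criterion but tolerates a lower dose counts as intolerant, or how that subject enters the dose assignment. Those passages must be reconciled.

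The consequence is modest. No power claim fails, and the upper limit for an SD moves only from 1.46 to 1.50 times the estimate if n falls from 20 to 18. The change is still worth making, because the stated size is optimistic and the balance of a very small factorial should not be left to an unstated mechanism.

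**What to change.** In section C.5:

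1. Say whether 20 is the number entering the run-in or the number assigned to dose, and what happens to the count when a subject is lost in the run-in.
2. If 20 is the number entering, restate 10 per dose and 5 per cell as maxima. Any expected figure (about 18 to 19 assigned, 4 to 5 per cell) should carry its assumption of 5% to 8% loss. If 20 is the number assigned, the totals in C.1 and F.1 must be larger: to expect 20, 20/0.95 = 21.1 and 20/0.92 = 21.7, so 22 entering in either case.
3. Randomise dose within each vitamin C group among run-in completers, from a list stratified by vitamin C group.
4. Report the number lost in the run-in by vitamin C group.

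The cost is a few sentences and a stratified list. If 20 remains the number entering, no extra subjects are needed, and the only downside is a slightly less favourable stated cell size.

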Wave reflections can be markedly reduced by organic nitrates, which dilate middle-sized muscular arteries even at doses that do not substantially reduce brachial blood pressure. Our overarching hypothesis is that reducing arterial wave reflections with organic nitrates will reduce LV hypertrophy (a precursor to HF), fibrosis and improve myocardial function in subjects with CKD, independently of blood pressure reduction. Our ultimate goal is to perform an RO1-funded double-blind, parallel-arm, placebo-controlled randomized clinical trial that will enroll patients with CKD and randomize them to either sustained-release isosorbide mononitrate therapy (SR-ISMN) or placebo for 24 weeks.

In this R56-funded study, we aim to obtain key preliminary data for an RO1 resubmission to accomplish a phase IIb randomized controlled trial to test our hypothesis. We wish to obtain: (1) preliminary data regarding the variability in the change of our endpoints in response to our intervention in this specific population; (2) Preliminary data regarding the effects of ISMN on blood pressure vs. wave reflections at different doses; (3) Data supporting the feasibility and local expertise to implement a biomarker discovery approach using proteomics. Our specific aims are:

PRIMARY AIMS: to assess the variability in the response and to perform a dose-response assessment in the degree of change in central hemodynamics and cardiac endpoints with Targeting Central Hemodynamics in CKD Pilot Study
Protocol Version 003, February 15, 2016

ISMN therapy in this population. We propose to administer 3 different doses of SR-ISMN (30, 60 and 120 mg of SR ISMN daily) to 20 subjects with CKD, in order to accomplish the following co-primary aims:

- 1a. To assess the variability in the change in **LV mass** with ISMN administration (**in order to support aim 1a of our eventual RO1-funded trial**). LV mass will be measured with steady-state free precession cardiac MRI.
- 1b. To assess the variability in changes in **diffuse myocardial fibrosis** with ISMN administration, using T1-mapping MRI techniques.⁵⁻¹²
- 1c. To assess the variability in changes in **myocardial systolic and diastolic function** with ISMN administration, assessed via systolic strain (measured with displacement encoded MRI, DENSE) and early diastolic mitral annular velocity (measured with tissue Doppler echocardiography), respectively.

SECONDARY AIMs:

[figure not shown]

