All data collected in this trial will be housed inside of a locked cabinet in the office space of the research staff, located at Ravdin 2 (Cardiovascular Institute).

C.8. Early termination

Subjects who withdraw due to intolerable adverse events or other safety concerns, or simply because they no longer wish to participate in the trial, will undergo a termination visit in which we will document: (1) vital signs; (2) compliance with the medications, including pill count; (3) Adverse effects. (4) specific reason for withdrawal.

D. Statistical Considerations

All study outcomes are continuous measures, thus, least-square regression models will be used to estimate effect sizes associated with each intervention. For the run-in phase, we will use mixed models to assess within subject changes to 30- 60 and 120 mg, and also to assess the effect of ascorbic acid on this response.

Analysis of the changes at 24 weeks between the study arms will also be assessed with mixed models to assess the following: (1) whether there are any significant within group changes in the outcome measures (from baseline to the final visit) in response to nitrate therapy at 30, 60 or 120 mg; (2) To test whether the outcome improvement in response to combination therapy is different between the 2 doses; (3) Whether vitamin C appears to have any effect on the responses. We recognize that this is a pilot study and therefore we will pay particular attention to the variability in the response and will interpret trends conservatively, particularly when confidence intervals are wide enough to be inconclusive. We note that, even though there is limited power for the inferential analyses, the data from this study will be critical to perform power calculations and propose a definitive trial, as per the aims of our R56 award. MRI endpoints will involve only 2 measures (baseline Targeting Central Hemodynamics in CKD Pilot Study

Protocol Version 003, February 15, 2016

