and 24-weeks). However, echocardiographic and tonometry measures will involve three measurements per subject during the long-term phase (baseline, 12-week and 24-week visit). These will be modeled for intervention effects using general linear modeling on the intent-to-treat population.^{64, 65} Subject-specific intercepts and slopes will be included as random effects; variability in the actual timing of assessments will be explicitly included in the mixed model by analyzing time as a random effect. Individual growth parameters will be modeled as a function of group, time, and the interaction of group and time. Differences in reflection magnitude over time will be examined via inferential testing of the “group by time” interaction term. Restricted maximum likelihood estimation will be used, and an appropriate covariance matrix will be specified. Linear and quadratic mixed models will be examined. The Akaike information criterion⁶⁶ will be used to evaluate overall model fit and to select the best-fitting longitudinal change pattern. For dropouts, the mechanism for missingness will be evaluated. If the number of subjects lost to follow-up is small and the missing observations can be documented as being missing at random (MAR) or missing completely at random (MCAR), analyses will be performed using the complete observed data. More complex approaches will be considered, such as random pattern-mixture models if necessary.^{67, 68} Sensitivity analyses for these models will be performed.⁶⁹ We will use parsimonious linear models to assess whether the reduction in reflection magnitude predicts the improvement in individual outcomes (LV mass, LV collagen volume fraction, LV diastolic relaxation velocity). Bootstrapping procedures will be used to obtain estimates of the effects and to test their significance via confidence intervals.⁷⁰ Analyses will be 1-tailed since we hypothesize specific directions to the relationships or changes in measured parameters between baseline and 24 weeks post-initiation of long-term therapy.

F. PROTECTION OF HUMAN SUBJECTS

F.1. RISKS TO THE SUBJECTS

Human Subjects Involvement and Characteristics

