If our hypothesis of a causal role is correct, this study may identify a potential intervention to induce reserve remodeling and prevent incident heart failure in CKD patients. Furthermore, if targeting wave reflections improves diastolic function, LV remodeling and the clinical status of CKD patients, this would lead to a better understanding of the mechanisms that lead to, or contribute to, cardiac dysfunction in CKD, which will accelerate the discovery of new treatments for this condition.

G. DATA AND SAFETY MONITORING PLAN

1. Adverse events

The Principal Investigator will be responsible for ensuring that all adverse events are noted, followed and reported to the IRB and DSMB as appropriate. The PI will continuously supervise all aspects of the study and review the records of the study subjects following each visit and at the end of their participation. Any adverse events (AE) will be rated on a 0-5 scale (0-no AE; 1-mild AE, no treatment required; 2-moderate AE that responds to treatment; 3-severe AE that would limit normal activities and require a prolongation of hospitalization; 4-life-threatening or disabling AE; 5-Fatal AE). Any AE rated ≥ 3 will be immediately reported to the IRB. All AEs will be reported to the IRB on an annual basis. In the case of a serious AE, the IRB will make a determination about the necessity to modify the protocol, include additional information in the consent form, inform previous participants, temporarily hold enrollment of patients, or terminate the study. All study procedures and cumulative adverse events are subject to full committee review at least yearly.

Adverse events known to be associated with ISMN include:

- Headache
- Mild dizziness
- Warmth, redness, or tingly feeling under skin
- Pounding heart beat
- Dry mouth
- Nausea/Vomiting
- Sweating
- Feelings of passing out
- An allergic reaction to this drug is very rare, but could manifest as hives, difficulty breathing, or swelling of the face, lips, tongue, or throat.
- Symptomatic hypotension.

Adverse effects that may be associated with vitamin C include:^{54, 55}

- Diarrhea
- Nausea
- Vomiting
- Heartburn
- Stomach cramps
- Headache

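### Section D item (1) labels 24-week change from baseline a response to nitrate therapy, but with no nitrate-free arm it can reject only no change from any cause

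*Combined protocol and SAP*

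**What the plan says.** Section C.1 describes the study: "This is a pilot study in which we will study 20 subjects with CKD". All of them enter the run-in: "We will administer 30 mg for 1 week, followed by 60 mg for 1 week, followed by 120 for 1 week". After that, "we will randomly assign subjects to receive either 60 or 120 mg of SR-ISMN" for a further 21 weeks. Vitamin C is given to half. Section C.5 sets this out as a 2x2 factorial with 5 subjects per cell and 10 per dose, open label with blinded endpoint assessment. No subject is without nitrate at any time after baseline.

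For the 24-week data, Section D lists three questions. The first is "1) whether there are any significant within group changes in the outcome measures (from baseline to the final visit) in response to nitrate therapy", followed by the doses. The second compares the two doses and the third looks at vitamin C. On sidedness, Section D says: "Analyses will be 1-tailed since we hypothesize specific directions to the relationships or changes in measured parameters between baseline and 24 weeks". It gives no alpha level.

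Section D also says that trends will be interpreted conservatively, particularly where confidence intervals are wide. The specific aims and the end of Section B name the variability of change as what the pilot is to supply for later power calculations.

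**The concern.** Item (1) attaches a cause to a before-after difference. That holds only if nothing other than ISMN moves the endpoint over 24 weeks, and the plan neither ensures this nor adjusts for departures from it. Inclusion criterion (3) in Section C.3 asks for stable background therapy for more than 30 days at entry; no stability rule or adjustment is stated for the 24 weeks that follow. Section B reports that standard antihypertensive drugs alter wave reflections in some patients, unpredictably and in either direction, and that reductions went with LV mass regression. Subjects also know that they are on active drug. Blinded reading guards against reader bias, but not against real change from these other sources.

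At stake is the reading of the 24-week result. A significant mean change in LV mass, fibrosis or relaxation velocity would, under the plan's wording, be called a response to nitrate. The definitive trial is to "randomize them to either sustained-release isosorbide mononitrate therapy (SR-ISMN) or placebo for 24 weeks", so the effect it estimates is a difference from placebo, which item (1) cannot estimate. The conservative-interpretation sentence does not cover this, because it addresses imprecision. Drift is a bias, and a narrow interval would make the misattribution look firmer.

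The point concerns the baseline-to-week-24 test only, not the run-in dose comparisons.

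**Working it through.** **Plan's own figure.** There is none to reproduce. Section D gives no alpha, SD, effect size or power. The allocation is consistent: 4 cells × 5 = 20 and 2 doses × 10 = 20.

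**What each contrast estimates.** For a subject on dose k, let D be the week-24 value minus baseline. Write E(D) = δₖ + γ, where δₖ is the effect of ISMN at dose k and γ is change from any other cause, common to all subjects.

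- Item (1): the null tested is δₖ + γ = 0. It matches no response to nitrate only if γ = 0.
- Item (2), 60 vs 120 mg: (δ₁₂₀ + γ) − (δ₆₀ + γ) = δ₁₂₀ − δ₆₀. The common γ cancels. The same holds for vitamin C vs none, and for a group-by-time interaction.
- SD of change: adding a constant γ to every D leaves it unchanged.

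**Size for item (1).** From the plan: n = 20 pooled, n = 10 per dose, 1-tailed. Assumed: alpha 0.05, normal change scores, δₖ = 0, and γ = d × SD of change. A one-sample t-test on D stands in for the mixed model. The rejection probability is P(T > t₀.₉₅), where T is non-central t with n − 1 degrees of freedom and non-centrality d√n. Critical values are 1.729 (n = 20) and 1.833 (n = 10). Positive d is drift in the hoped-for direction.

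| d | d√20 | rejects, n = 20 | d√10 | rejects, n = 10 |
|---|---|---|---|---|
| −0.3 | −1.342 | 0.2% | −0.949 | 0.6% |
| −0.2 | −0.894 | 0.6% | −0.632 | 1.3% |
| −0.1 | −0.447 | 1.9% | −0.316 | 2.6% |
| 0 | 0 | 5% | 0 | 5% |
| 0.1 | 0.447 | 11% | 0.316 | 9% |
| 0.2 | 0.894 | 22% | 0.632 | 14% |
| 0.3 | 1.342 | 36% | 0.949 | 22% |

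Favourable drift of 0.084 SD (n = 20) or 0.124 SD (n = 10) is enough to double the nominal 5%.

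**Check on the allocated contrast and the SD.** In 100,000 simulated trials with 10 per dose and no drug effect, the 60 vs 120 mg comparison rejected in 4.9%, 5.1%, 4.9% and 5.0% at common drift of 0, 0.2, 0.5 and 0.8 SD. The average estimated SD of change was 0.985 to 0.986 of the true value at every drift, so the mean shift did not affect it.

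**The case against.** Five things can be said for the plan.

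- **It is an open pilot.** The parenthesis in item (1) says plainly that the quantity is change from baseline to the final visit, and Section B says that a randomised trial is needed to settle causality. This stands, but it does not alter the causal label that item (1) puts on the test.
- **The drift is hypothetical.** The documents give it no size or sign, and Section B says that reflection magnitude rose in some subjects on standard therapy. This stands, which is why the table runs in both directions. A reader might infer that the test is bound to produce false positives; with unfavourable drift it rejects less than 5% of the time.
- **Power calculation.** Section D says that "least-square regression models will be used to estimate effect sizes associated with each intervention", and later that the pilot data will be critical for power calculations. A reader might infer that the within-group mean change will be the planning effect of the placebo-controlled trial. The documents do not say so. Where they name the input, it is variability, which a common shift does not bias.
- **Section F.4.** The statement that "this study may identify a potential intervention to induce reserve remodeling and prevent incident heart failure in CKD patients" could be read as a claim resting on item (1). It is conditional on the causal hypothesis being correct and sits in the human-subjects section, so it is not an analysis claim and needs no change on this account.
- **Other limits on bias.** Endpoint assessment is blinded. Eligibility rests on an earlier clinical scan with a separate baseline MRI, so regression to the mean from measurement error should fall mostly before baseline. Both stand, but neither deals with background-therapy changes or time trend.

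It may also be said that a confidence interval carries the same information as the test. Numerically it does; what changes is that the interval is presented as change during treatment, without attribution.

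**Conclusion.** The point holds as a fault in how item (1) is specified and labelled. With every subject on ISMN, the 24-week within-group test addresses change from any cause, and the plan would have a significant result described as a response to nitrate. How far this would mislead is unknown. The figures of 11% to 36% (n = 20) and 9% to 22% (n = 10) rest on favourable drift of 0.1 to 0.3 SD, alpha of 0.05 and no drug effect, none of which the documents supply. The primary aim, the SD of change, and the dose and vitamin C contrasts are not biased by a common shift. No figure in the protocol changes.

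**What to change.** Replace item (1) in Section D with:

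> Within-group change from baseline to week 24 will be reported by dose and pooled as mean change during ISMN, with a confidence interval and SD. It will not be described or tested as a response to ISMN, because there is no nitrate-free comparison. Treatment-effect statements at 24 weeks will be limited to the allocated contrasts (60 vs 120 mg; vitamin C vs none).

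As a clarification only, since the plan does not say otherwise, add that the SD of change, not the within-group mean change, feeds the power calculation of the definitive trial.

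The cost is protocol wording: no change to sample size, visits or procedures. The downside is that the study gives up a nominal 24-week p-value for an ISMN effect, which its design cannot support.
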